6 STUDY DESIGN

6.1 Description

This is a prospective randomized trial comparing the biopsy specimen adequacy (SA) of 19-g FNA versus 19-g FNB needle for EUS-LB.

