The left lobe is described as liver parenchyma identified a few centimeters below the gastroesophageal junction with the echoendoscope torqued clockwise. The right lobe is considered the large area of liver tissue can be seen through the duodenal bulb, near the gallbladder [37]. The stylet is removed, heparin flushed through the needle lumen, and the suction device set and attached to the needle hub. The prepared needle is then inserted into the echoendoscope. A transgastric approach will be used to obtain samples from the left lobe of the liver; a transduodenal approach, with the linear echoendoscope positioned in the duodenal bulb, will be used to obtain samples from the large amount of liver parenchyma seen in that location. Once adequate liver parenchymal penetration will be achieved with the needle (~2-6 cm), full suction will be applied with a 20-mL vacuum syringe. One pass consists of a total of 7 to 10 to-and-fro needle motions with the fanning technique applied under direct and continuous endosonographic visualization of the tip of the needle.

The needle will then be removed from the echoendoscope. The specimen will be pushed from the needle with the stylet directly into a microseive, and blood washed from the specimen with a gentle saline rinse. The endosonographer looks for multiple pieces of light brown tissue approximately 5 to 15 mm in length. The tissue cores are then “floated” off the microseive into formalin solution. Heparin is flushed through the needle lumen prior to the next pass. The biopsy process is then repeated on the opposite liver lobe. A pass per liver lobe will be performed in each patient; using the standard 19-g EUS-FNA needle or the 19-g EUS FNB

Date Last Modified: 10/2/2017

IRB # 2017-0391

CONFIDENTIAL AND PROPRIETARY

needle. All patients are closely observed in the recovery area for 1 hour after the procedure, as per our standard policy. Patients will be followed-up with by a phone call the next day and at 1 week after the procedure, as per standard of care.

Sample Processing

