6.8.1 Statistical Analysis Plan

Assuming the 19-g FNB needle has a success percentage of 98% (ie, ≥ 5 portal triads), and margin over FNA needle of 5% (98% vs. 93%), the study needs to evaluate 32 patients to achieve 80% power for a 1-sided non-inferiority test. This also assumes each patient provides 2 specimens. If the margin is increased to 10% (98% vs. 88%), then the study needs to evaluate 18 patients to achieve 80% power.

Descriptive statistics will be utilized to represent continuous and categorical variables, with results expressed as medians with ranges. Multiple comparisons between the aggregate tissue length and CPT yield from bilobar, left lobe only, and right lobe only biopsies will be carried out using the Mann-Whitney-Wilcoxon test. A P-value of <0.05 will be considered statistically significant.

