6.8.2 Statistical Power and Sample Size Considerations

The purpose of this study to determine if the 19-g FNB EUS needle provides liver cores equal or superior to 19-g FNA needle for histologic interpretation. A few preliminary cases utilizing the 19g core needle have been found to provide adequate cores. It is felt that 32 cases collected prospectively should be adequate to learn how the 19g FNB needle compares to the 19g FNA needle in different patients with different liver conditions.

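### Section 6.8.1 sizes the trial on a one-sided non-inferiority test but does not carry that test into the analysis, and 32 patients do not give the stated 80% power for the 5-point margin

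*Combined protocol and SAP*

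**What the plan says.** Section 6.1 describes a randomised trial "comparing the biopsy specimen adequacy (SA) of 19-g FNA versus 19-g FNB needle for EUS-LB". Section 4.1 predicts that the needles will be similar, and section 6.8.2 asks whether the FNB needle "provides liver cores equal or superior to 19-g FNA needle for histologic interpretation".

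The first paragraph of section 6.8.1 defines success as 5 or more portal triads, sets FNB success at 98%, and gives a "margin over FNA needle of 5% (98% vs. 93" (the quotation stops before the percent sign). It says that 32 patients give "80% power for a 1-sided non-inferiority test", and adds: "This also assumes each patient provides 2 specimens". A 10-point alternative (98% vs 88%) is said to need 18 patients.

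The second paragraph holds all the analysis text in the document. It calls for descriptive medians and ranges, and for comparisons of "aggregate tissue length and CPT yield from bilobar, left lobe only, and right lobe only biopsies will be carried out using the Mann-Whitney-Wilcoxon test". It ends: "A P-value of <0.05 will be considered statistically significant".

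On specimens, section 6.5 says: "A pass per liver lobe will be performed in each patient".

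**The concern.** A non-inferiority claim needs a confidence bound, or an equivalent test, set against a margin. The Mann-Whitney-Wilcoxon test uses no margin, and it is applied to length and CPT yield rather than to the success proportion that sized the trial. It therefore cannot show that one needle's success rate lies within 5 points of the other's, so the plan followed as written cannot support a conclusion of similar, or of equal or superior.

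If the non-inferiority test is meant as the needle analysis, it cannot be run without further choices. No alpha is tied to it, because the 0.05 threshold follows the Mann-Whitney sentence and has no stated sidedness. Two margins appear. The phrase 98% vs 93% does not separate the margin from the assumed true difference. Nothing says whether the specimen or the patient is the unit. If these items stay open, they can be settled after the data are seen.

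**Working it through.** **1. Sizing text against analysis text (both in section 6.8.1)**

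| Item | Sizing paragraph | Analysis paragraph |
|---|---|---|
| Contrast | FNB vs FNA | Lobe sets; no needle contrast named |
| Outcome | Success, 5 or more portal triads | Aggregate length, CPT yield |
| Test | One-sided non-inferiority | Mann-Whitney-Wilcoxon |
| Margin | 5 points (10 as alternative) | None |
| Threshold | None given | P<0.05, sidedness not given |

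The gap in the analysis shows from the text alone. The arithmetic below concerns the 80% power.

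**2. The plan's own sample size**

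Inputs from section 6.8.1: FNB 98%, FNA 98% or 93% (both readings of the phrase), margin m = 0.05, power 80%, two specimens per patient. Assumed: 1:1 allocation (no ratio is stated), one-sided alpha 0.05 and independent specimens. With two arms and two specimens per patient, the number of specimens per arm equals the total number of patients.

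n per arm = (1.645 + 0.842)² × [pB(1−pB) + pA(1−pA)] / (pB − pA + m)², where the first factor is 6.183.

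- 98/98: 6.183 × 0.0392 / 0.0025 = 96.9, so 97 patients.
- 98/93: 6.183 × (0.0196 + 0.0651) / 0.01 = 52.4, so 53 patients.
- 10-point margin: 25 patients (98/98) or 20 (98/88).

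The plan states 32 and 18. No single standard method that was tried gives both figures.

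**3. Power at 32 patients, unpooled normal approximation, 32 specimens per arm**

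- 98/98: SE = √(0.0392/32) = 0.0350; 0.05/0.0350 − 1.645 = −0.216; power 41%.
- 98/93: SE = √(0.0847/32) = 0.0514; 0.10/SE − 1.645 = 0.299; power 62%.

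**4. Exact power of the score test**

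The normal approximation is rough near 98%, so the score test was enumerated:

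Z = (observed FNB − FNA difference + m) / √{[p̃B(1−p̃B) + p̃A(1−p̃A)]/n}

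Here p̃B and p̃A are the maximum-likelihood rates under p̃B = p̃A − m. Power is the binomial probability of all outcomes with Z at or above the critical value.

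If both specimens come from one needle with within-patient correlation ρ, the effective number per arm is 32/(1 + ρ). This is 32 when they are independent and 16 when they are fully correlated.

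| Margin, one-sided alpha | True FNB/FNA | 32 per arm | 16 per arm |
|---|---|---|---|
| 5 points, 0.05 | 98/98 | 26% | 3% |
| 5 points, 0.05 | 98/93 | 61% | 23% |
| 5 points, 0.025 | 98/98 | 7% | 0.3% |
| 5 points, 0.025 | 98/93 | 41% | 7% |
| 10 points, 0.05 | 98/98 | 57% | 20% |
| 10 points, 0.05 | 98/88 | 93% | 70% |

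**5. What the 5-point margin would demand of the data (alpha 0.05)**

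With no failures in either arm, the score lower bound is −z²/(n + z²). At 32 per arm this is −2.706/34.706 = −7.8 points; at 16 per arm it is −2.706/18.706 = −14.5 points. Equal perfect results would therefore miss a 5-point margin. At 32 per arm, FNB 32/32 against FNA 31/32 gives −4.8 points and passes; 31/32 against 31/32 gives −10.1 points and fails.

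**The case against.** The non-inferiority test is named, with its sidedness, outcome and candidate margins, in a section headed as the analysis plan, while power has its own section, 6.8.2. One can fairly read it as the intended needle analysis, with the second paragraph covering description and lobe comparisons. This stands in part: the test is incompletely specified rather than absent. But the paragraph that says what will be done does not take it up, and its alpha, bound method and unit are missing.

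A reader might infer that the investigators mean to report a non-significant Mann-Whitney result as similarity. The documents nowhere say so, and the literal wording names lobe sets. That misuse is possible only if the test compares needles.

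The power figures depend on the test. At 98/98 with 32 per arm, the score test gives 26%, the normal approximation 41%, and an enumerated unpooled Wald rule, unreliable near 100%, 53%. All are below 80%. The 16-per-arm case also assumes that both of a patient's specimens come from one needle. The one-pass-per-lobe sentence in section 6.5 supports this, but the sample-processing text there, which has samples from the different needles submitted separately, leaves some doubt. Allocation by lobe would give a paired comparison, and the 16-per-arm figure would not apply.

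Finally, naming the test neither causes nor cures low power. That is so; the power needs its own correction in the same section.

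**Conclusion.** The point holds in two parts. First, on the text alone, section 6.8.1 does not carry its sizing test into the analysis, and the tests that it does state use no margin and do not address the success proportion. Second, the stated 80% power is not delivered for the 5-point margin. Under 1:1 allocation, one needle per patient, a score test and one-sided alpha 0.05, it is 26% or 61% with independent specimens and 3% or 23% with fully correlated ones, depending on whether FNA is truly at 98% or 93%. Alpha 0.025 lowers all four.

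Two stronger readings are not supported. The documents do not show that the non-inferiority test was abandoned or replaced. Nor is the trial short of 80% power in every scenario: for the 10-point margin at 98/88, with 32 independent specimens per arm and alpha 0.05, power is 93%. The point must be fixed because the main comparison otherwise has no usable decision rule.

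**What to change.** Add to section 6.8.1: 'The needle comparison is the FNB minus FNA difference, by randomised needle, in the proportion with 5 or more portal triads. A one-sided 95% score-type lower confidence bound, allowing for two specimens within a patient, is compared with the 5-point margin; non-inferiority is declared only if the bound lies above −5 points. A non-significant Mann-Whitney P-value is not evidence of similarity.'

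Alpha 0.05 is the plan's only stated threshold, and 5 points is the margin tied to 32 patients. Name the clustering method, for example a cluster-adjusted effective sample size or a patient-level analysis. Say whether the Mann-Whitney tests compare needles or lobes, and how this outcome relates to the first-listed primary endpoint in section 6.6, histologic diagnosis.

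Then restate the 80% power with its assumptions, or report the trial as estimation, with n/N, percentages and confidence intervals by needle.

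The cost is a few sentences and no new data. The price is candour: the rule exposes the low power and, at 32 per arm, would not be met even if neither needle failed. The sponsor should settle this before the data are seen.

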6.8.2 Statistical Power and Sample Size Considerations

The purpose of this study to determine if the 19-g FNB EUS needle provides liver cores equal or superior to 19-g FNA needle for histologic interpretation. A few preliminary cases utilizing the 19g core needle have been found to provide adequate cores. It is felt that 32 cases collected prospectively should be adequate to learn how the 19g FNB needle compares to the 19g FNA needle in different patients with different liver conditions.

6.9 Data Management

6.9.1 Data Collection and Storage

EPIC electronic health records database will allow for availability of demographic data and office-based follow-up records. ProVation MD software information will provide details regarding endoscopic parameters and intervention performed.

Electronic records gathered for study purposes will only be available to study investigators and will be stored on an encrypted hard drive on a computer. Data will initially be entered with PHI attached so that all information can be obtained. Once all data collection is complete identifiers will be removed and random number assigned to the patients.

6.9.2 Records Retention

Records shall be retained for a total of 6 years as per Geisinger policy

7 SAFETY MONITORING

7.1 Adverse Event Reporting

Clinical adverse events (AEs) will be monitored throughout the study. All AEs will be reported to the institutional review board (IRB) regardless of whether they are considered study related. The date and time of onset and outcome, course, intensity, action taken, and causality to study treatment will be assessed by the study PI. In the event of a serious AE (SAE), this will be reported to the Geisinger IRB (GIRB) according to the GIRB guidelines. All other AEs will be summarized and submitted to GIRB during continuing review.

7.2 Definitions

An **adverse event** (AE) is any untoward, undesired, or unplanned event in the form of signs, symptoms, disease, or laboratory or physiologic observations occurring in a person given a test article or in a clinical study. The event does not need to be causally related to the test article or clinical study.

[Include as applicable to study]

An AE includes, but is not limited to, the following:

- Any clinically significant worsening of a preexisting condition.
- An AE occurring from overdose of a test article, whether accidental or intentional. Define overdose for each test article here or in the Overdose section. Overdose is a dose greater than

Date Last Modified: 10/2/2017

IRB # 2017-0391

CONFIDENTIAL AND PROPRIETARY

that specified in the protocol. OR Overdose is a dose greater than that specified in the investigator's brochure/label. OR define overdose

- An AE occurring from abuse (e.g., use for nonclinical reasons) of a test article.
- An AE that has been associated with the discontinuation of the use of a test article.
- For reports from post marketing studies, any failure of expected pharmacologic action of a test article. For over-the-counter products, the recommended daily dose must be administered before failure of expected pharmacologic action can be attributed.

A **serious adverse event (SAE)** is an AE that:

- Results in death.
- Is life-threatening (see below).
- Requires inpatient hospitalization or prolongation of an existing hospitalization (see below).
- Results in a persistent or significant disability or incapacity (see below).
- Results in cancer.
- Results in a congenital anomaly or birth defect.
- Additionally, important medical events that may not result in death, be life-threatening, or require hospitalization may be considered SAEs when, based on appropriate medical judgment, they may jeopardize the subject and may require medical or surgical intervention to prevent one of the outcomes listed in this definition. Examples of such events include allergic bronchospasm requiring intensive treatment in an emergency room or at home, blood dyscrasias or convulsions that do not result in hospitalization, or development of drug dependency or drug abuse.

Life-threatening refers to immediate risk of death as the event occurred per the reporter. A life-threatening experience does not include an experience, had it occurred in a more severe form, might have caused death, but as it actually occurred, did not create an immediate risk of death. For example, hepatitis that resolved without evidence of hepatic failure would not be considered life-threatening, even though hepatitis of a more severe nature can be fatal. Similarly, an allergic reaction resulting in angioedema of the face would not be life-threatening, even though angioedema of the larynx, allergic bronchospasm, or anaphylaxis can be fatal.

Hospitalization is official admission to a hospital. Hospitalization or prolongation of a hospitalization constitutes criteria for an AE to be serious; however, it is not in itself considered an SAE. In absence of an AE, a hospitalization or prolongation of a hospitalization should not be reported as an SAE by the participating investigator.

Date Last Modified: 10/2/2017

IRB # 2017-0391

CONFIDENTIAL AND PROPRIETARY

In addition, a hospitalization for a preexisting condition that has not worsened does not constitute an SAE.

Disability is defined as a substantial disruption in a person's ability to conduct normal life functions.

If there is any doubt about whether the information constitutes an SAE, the information is treated as an SAE.

A **protocol-related adverse event** is an AE occurring during a clinical study that is not related to the test article, but is considered by the investigator or the medical monitor (or designee) to be related to the research conditions, i.e., related to the fact that a subject is participating in the study. For example, a protocol-related AE may be an untoward event occurring during a washout period or an event related to a medical procedure required by the protocol.

Other Reportable Information. Certain information, although not considered an SAE, must be recorded, reported, and followed up as indicated for an SAE. This includes:

- Pregnancy exposure to a test article, except for exposure to prenatal vitamins. If a pregnancy is confirmed, use of the test article must be discontinued immediately. Information about pregnancy exposure includes the entire course of pregnancy and delivery, and perinatal and neonatal outcomes, even if there are no abnormal findings. Both maternal and paternal exposure are considered other reportable information. For exposure involving the female partner of a male subject, the necessary information must be collected from the subject, while respecting the confidentiality of the partner.
- Lactation exposure to a test article with or without an AE.
- Overdose of a test article as specified in this protocol with or without an AE. Baby formula overdoses without any AEs are excluded.
- Inadvertent or accidental exposure to a test article with or without an AE.

7.3 Recording and Reporting

A subject's AEs and SAEs will be recorded and reported from the signing of the informed consent form to 1 week from EUS-LB Procedure.

7.4 Serious Adverse Event Reporting

[name] will notify GIRB of all study SAEs in accordance with policy guidelines. If an SAE has not resolved at the time of the initial report, a follow-up report including all relevant new or reassessed information (e.g., concomitant medication, medical history) will be submitted to GIRB. An SAE will be followed until either resolved or stabilized.

8 PROTECTION OF HUMAN SUBJECTS

8.1 Informed Consent

The investigator will provide for the protection of the subjects by following all applicable regulations. The informed consent form will be submitted to the IRB for review and approval.

Before any procedures specified in this protocol are performed, a subject must:

- Be informed of all pertinent aspects of the study and all elements of informed consent.
- Be given time to ask questions and time to consider the decision to participate.
- Voluntarily agree to participate in the study.
- Sign and date an IRB-approved informed consent form.

8.2 Protection of Human Subjects Against Risks

Potential Risks due to Study participation -

A potential risk is loss of the patients' privacy and loss of the confidentiality of their data.

Upper endoscopy possesses a 0.0004-0.00009% risk of perforation, and less than 0.5% risk of bleeding [38]. Adverse events described with the EUS and fine needle aspirate possess a complication rate of 1.72% in prospective studies and 0.64% in retrospective studies. The risk of perforation for EUS is roughly 0.06% and bleeding 0.13%. There have not been established increased risks of complication in patients who undergo EUS with different biopsy needles. However, the 19g needle is the standard needle size in use for EUS-LB, and has been found to be very safe.

Potential Benefits

Included patients are already undergoing the procedure to make a clinical diagnosis of the liver abnormality, and also have the benefit of requiring only one endoscopic procedure to evaluate digestive system problems while at the same time obtaining liver biopsy. As the potential complications with EUS-LB seem to be lower than other means of liver biopsy, a potential benefit is sparing patients from the complications caused by other methods of liver biopsy. This study shall also benefit future patients by providing data regarding prediction of success for EUS-LB with 19-g FNA versus 19-g FNB needles.

Date Last Modified: 10/2/2017

IRB # 2017-0391

CONFIDENTIAL AND PROPRIETARY

Risk: Benefit Ratio

A potential risk in this study involves loss of confidentiality. The use of password protected data storage, removal of PHI and assignment of randomly generated patient number and limitation of data to the study investigators shall limit this risk. Additionally, there is a small risk of perforation or bleeding in diagnostic endoscopy and EUS-LB. These risks are outweighed by the benefit of procuring a diagnosis behind their liver-related abnormality.

Procedures to Maintain Privacy and Confidentiality

As exposure of confidential information is a potential risk, subject identifiers shall not be recorded and subjects shall be given a randomly generated number. The project investigators shall be the only ones with access to the study data, which shall be kept on a password protected/locked Geisinger computer. All data will be destroyed at the completion of this study's manuscript completion.

Vulnerable Subjects

It is possible that terminally ill patients may be involved in this study. This study will however not involve direct intervention and not impact/delay the procedure for which they are undergoing. The observational nature of the study and the subject's ability to exclude them from the study at any time shall be reinforced by the PI/Co-I.

No individuals who require substituted consent shall be involved in this study, nor any children.

Compensation to Subjects

No compensation shall be granted to subjects as this is an observational study and does not deviate from the standard of care.

Treatment of Research-Related Injuries

Potential procedure-related injuries would include perforation or bleeding, which would be managed in a standard fashion. There are no additional "research-related" injuries. Any injuries in the study cohort will be a result of risks inherent to the procedure. This is always explained during the consent process for the procedure and is the standard of care.

